**List of Abbreviations**

4D: 4 Dimensional  
3D: 3 Dimensional  
CT scan: Computed tomography scan  
MR Scan: Magnetic Resonance Imaging Scan  
NSCLC: Non Small Cell Lung Cancer  
SCLC: Small Cell Lung Cancer  
SUV value: Standardized Uptake Values  
Gy: Gray  
CTV: clinical tumor volume  
PTV: planning target volume  
GTV: gross tumor volume  
ITV: internal tumor volume  
PI: Principal Investigator  
AE: Adverse Event  
SAE: Serious Adverse Event  
GI: Gastrointestinal  
IRB: Institutional Review Board  
ORP: Office of Research Protection  
HRPO: Human Research Protection Office

## Quantification of Tumor and Organ at Risk (OAR) Volume and Motion Path Changes during Definitive Photon or Proton Beam Radiotherapy

### PROTOCOL OVERVIEW

In recent years, conformal techniques have been developed that allow for precise delivery of radiotherapy to the primary tumor and regional lymphatics while minimizing the dose to normal tissues. These approaches are predicated upon precise anatomic localization of the regions to be irradiated. Unfortunately, at present, most conformal treatment delivery approaches do not account for changes in tumor volume, tumor motion or changes in patient anatomy during the time course of definitive radiotherapy. Proton beam radiotherapy can potentially allow for ultra-precise delivery of treatment due to the physical characteristics of the proton beam. Therapeutic proton beam radiotherapy allows for the elimination of exit dose and a significant reduction in the entrance dose to the patient while maximizing dose delivered to the tumor (Figure 1). However, accurate treatment delivery with proton beam radiation is predicated upon precise definition of tumor volume and location. Tumor volume reduction during definitive proton beam radiotherapy has resulted in significant dosing errors, with dose deposition in unintended regions (MDACC PTCOG 47). The purpose of this protocol is to quantify the extent of tumor volume, motion, and anatomic changes that occur during the tumor course of definitive photon beam radiotherapy. As both proton beam and photon beam radiotherapy have nearly identical biological efficacy, the changes observed during photon beam radiotherapy should closely approximate that which would likely be observed during proton beam irradiation.

**Quantification of Tumor and Organ at Risk (OAR) Volume and Motion Path Changes during Definitive Photon or Proton Beam Radiotherapy**

Figure 1: Comparison of Dose Deposition between Photon and Proton Beam Radiotherapy

**SPECIFIC AIMS/OBJECTIVES**

**Overall Aim**

To estimate the degree of tumor volume, tumor motion, and patient anatomy changes that occur during the time course of definitive photon and proton beam radiotherapy. We further intend to quantify the dosimetric error that would occur in patients receiving proton beam radiotherapy if these changes are not accounted for.

[figure not shown]
**Primary Aim**

To estimate the degree of tumor volume, tumor motion and patient anatomy change during treatment with photon beam radiotherapy using 4D or 3D CT Scans and/or a serial of MR Imaging.

**Secondary Aims**

To utilize the data generated from the photon or proton beam patients to simulate and estimate the degree of error if tumor volume, tumor motion path and patient anatomy changes are unaccounted for during treatment with proton beam radiotherapy by generating simulated serial proton plans with this data.

## METHODS/METHODOLOGY

**Quantification of Tumor and Organ at Risk (OAR) Volume and Motion Path Changes during Definitive Photon or Proton Beam Radiotherapy**

\*Baseline/eligibility procedures, including informed consent, may occur at any time from consultation until radiation therapy treatment begins.

All subjects' data will receive a standardized analysis. A descriptive analysis will be performed to determine tumor volume changes, tumor motion changes and patient anatomy changes. We will also evaluate the variations in the dose distribution to targeted volumes and normal tissues that occur with tumor and patient anatomy changes. These variations in dose distribution will be compared between photon treatment plans and proton treatment plans.

**ELIGIBILITY**

- Patients with biopsy proven NSCLC, SCLC, Head and Neck Cancer, Gastrointestinal cancer (including but not limited to colorectal and rectal cancers), or Gynecological malignancy requiring definitive radiotherapy with or without chemotherapy.

**REQUIRED SAMPLE SIZE**

- 30 patients per treatment site for a total of 120 patients.

**STUDY DESIGN**

- This is a pilot study to evaluate the changes in tumor volume, tumor motion, patient anatomy and dose distribution during the course of radiation treatment using up to weekly CT and/or MR Scans with the potential usage of contrast during the imaging procedure. We will analyze the effect of tumor changes and patient anatomy changes on radiation treatment efficacy.

## **1.0 ABSTRACT**

In recent years, conformal techniques have been developed that allow for precise delivery of radiotherapy to the primary tumor and regional lymphatics while minimizing the dose to normal tissues. Unfortunately, at present, most conformal treatment delivery approaches do not account for changes in tumor volume, tumor motion or changes in patient anatomy during the time course of treatment. Studies have shown that lung, head and neck, and gynecological tumors can change significantly during radiation treatment. Patients can lose significant weight during the radiation treatment, which can alter the patient's body habitus and anatomy. These tumor and anatomical changes can alter radiation dose distribution, resulting in higher radiation doses to normal tissue and lower radiation doses to target volumes. Adapting for changes in tumor motion, tumor volume and patient anatomy can therefore enhance radiation treatment efficacy and widen the therapeutic ratio. Because proton beams require precise target definition, accounting for tumor changes should be critical when using proton beam radiation treatment.

This is a pilot study to quantify the tumor and organ at risk volume and motion path changes that occur during definitive proton beam or photon beam radiotherapy. The patients will undergo CT scans in treatment planning position at the time of CT Simulation. Photon beam treatment plans and proton beam treatment plans will be generated from these images. Based on the location of the primary tumor, patients will undergo either up to weekly 3D or 4D CT and/or a serial of MR scans during treatment. These images will be compared to the initial CT and/or MR scans used for treatment planning and analyzed for changes in tumor volume and tumor anatomic location. At the end of treatment, the /serial images will be compared to the initial treatment planning images to quantify the changes in tumor volume and tumor motion during the course of radiation treatment. Each CT and/or MR scan will also be used to evaluate the changes in dose distribution to the target volumes and normal tissues that occur with the initial photon treatment plan and initial proton treatment plan. The changes in tumor volume, tumor motion and dose distribution during the course of radiation treatment will be analyzed to determine the effect of tumor changes on radiation treatment efficacy.

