## **2.0 BACKGROUND AND SIGNIFICANCE**

Radiation therapy is a form of treatment used to control many cancers including lung cancers, head and neck malignancies, cancers of the gastrointestinal tract and gynecological cancers. One important challenge of radiation treatment is the balance between delivering adequate radiation dose to the tumor while controlling for radiation induced toxicity. Radiation induced toxicity is caused by incidental radiation delivery to critical normal structures in proximity to the tumor. The amount of incidental radiation dose is dependent upon the tumor volume, location and margins needed to account for planning and setup error. The volumes are determined during radiation treatment planning and are based on patient imaging done during a simulation appointment prior to radiation treatment. In cancers with a propensity for movement secondary to respiratory motion, such as lung, and some gastrointestinal cancers, 4D CT planning is often implemented. This form of image guided treatment planning takes into account

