### **6.4. Study Calendar / Schedule**

Event	Baseline/Eligibility	Prior to RT Initiation	Weekly during RT
Informed Consent	X*	X*	
History and Physical	X	X	
Photon and Proton Treatment Planning and/or Baseline MR scan	X	X	
3D/4D CT and/or MR scans (determined by tumor location and treating physician)			X*
Blood Draw (prior to each imaging scan during RT)**		X	X

\* These are research specific procedures. All other procedures are standard of care.

\*\* Only if receiving contrast with imaging).

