### **6.6. *On Treatments***

Based on the primary tumor location and the discretion of the treating radiation oncologist, patients will undergo 3D/4D CT Scan (up to weekly) and/or MR Scan (minimum of 3).. The GTV, ITV and critical normal structures will be contoured on each up to weekly/serial scan. The up to weekly/serial GTV volume will be compared to the initial GTV volume to determine changes in tumor volume. Each GTV will be compared to the initial ITV volume to determine what percent of the GTV resides within the initial ITV. This value will be used to evaluate changes in tumor motion. Each ITV will be compared to the initial ITV. The initial photon treatment plan and proton treatment plan will be applied to the new scan. The amount of radiation dose to each GTV, ITV and critical normal structures will be recorded to determine the changes in dose distribution that occur as treatment progresses. **SUBJECTS WILL RECEIVE ALL SCANS IN THE RADIATION ONCOLOGY CLINIC OF THE UNIVERSITY OF PENNSYLVANIA.**

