### **9.3 *Objectives:* To determine changes over time in:**

1. tumor volume variables
2. tumor motion
3. patient anatomy
4. dose distribution to tumor and critical normal organs

**9.4 Endpoints:** To be measured at baseline and then weekly during 7-8 weeks of radiotherapy

1. GTV (gross tumor volume), the volume of the primary tumor visualized on the CT scan
2. ITV (interior tumor volume), the GTV expanded to include interior motion (i.e., breathing or swallowing) such that the tumor resides within the ITV during normal motion
3. CTV (clinical tumor volume), the ITV expanded to include microscopic disease (margins)
4. PTV (planning tumor volume), the CTV expanded by several mm, as determined by radiation dosimetry planning, PTV is considered the ultimate target volume

NOTE the relationship: GTV < ITV < CTV < PTV

5. Dose coverage: at each scan time point, determine the percent of the GTV which resides within the baseline ITV or CTV
5. patient weight and percent weight loss from baseline
6. Radiation dose to critical normal organs based on dose-volume histograms (i.e., 20 Gy to 50% of normal lung tissue)

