**9.5 Plans for Data Analysis: To be conducted within each stratum**

1. Tumor Volume: To determine the distributions of volume variables and percent change from baseline. At each scan time point, compute mean, median, range and standard deviation of these variables and plot mean values over time. To compare volume variables at baseline to the values at selected scan time points by paired Wilcoxon signed ranks test.
2. Tumor Motion: At each scan time point, compute mean, median, range and standard deviation of the dose coverage and plot mean values over time. To compare ITV or CTV variables at baseline to the GTV at selected scan time points by paired Wilcoxon signed ranks test.
3. Patient Anatomy: To determine the distribution of patient percent weight loss. At each scan time point, compute mean, median, range and standard deviation of percent weight loss and plot mean values over time.
4. Dose distribution: To determine the distributions of radiation dose to GTV, ITV and critical normal organs. To correlate radiation dose to normal organs with percent weight loss.
5. Conduct exploratory longitudinal analyses to examine changes over time in the 30 patients. Random effects linear regression models will be employed to estimate changes in variables over time clustered by patient. Natural log transformation will be applied prior to modeling.
6. To assess if changes in volume variables are clinically relevant and if so, identify the earliest time point at which re-calibration is warranted. Although it may not be possible to identify a single 're-calibration solution' for all patients in a particular stratum, we will attempt to identify the earliest scan time point at which the majority of patients have clinically important changes in tumor volume or location resulting in over-shoot of the target volume and/or increased dose exposure to normal organs.

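### Containment of the tumor in the baseline ITV or CTV starts at 100% by construction, so one trend through the planning scan and the later scans can show a decline during radiotherapy when there is none

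*Combined protocol and SAP*

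**What the plan says.** The Primary Aim is "To estimate the degree of tumor volume, tumor motion and patient anatomy change during treatment with photon beam radiotherapy". The Abstract (1.0) and Study Overview (4.0) make the initial planning images the reference; in the words of 1.0, "serial images will be compared to the initial treatment planning images to quantify the changes in tumor volume and tumor motion during the course". Section 2.0 places those images before treatment: target volumes are "based on patient imaging done during a simulation appointment prior to radiation treatment".

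Section 6.6 defines the motion measure: "Each GTV will be compared to the initial ITV volume to determine what percent of the GTV resides within the initial ITV". Section 9.4 repeats it as an endpoint, allows the baseline CTV as the alternative container, and gives the schedule for all endpoints: "To be measured at baseline and then weekly during 7-8 weeks of radiotherapy". Section 6.5 builds the ITV in 4D planning to contain the GTV and its breathing excursion, and 9.4 states that the volumes nest from GTV up to PTV. The photon and proton plans are made on the simulation CT and then applied to each later scan (6.5, 6.6).

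For analysis, 9.5 item 2 summarises containment at each scan and plots the means. Item 5 adds an exploratory model after log transformation: "Random effects linear regression models will be employed to estimate changes in variables over time clustered by patient". Item 6 looks for the earliest scan at which most patients show a clinically important change.

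The plan defines no reference scan at the first fraction, no limit on or recording of the time from simulation to first fraction, and no repeat scan or repeat contour from which noise could be estimated. The calendar (6.4) ticks "Photon and Proton Treatment Planning and/or Baseline MR scan" in two columns before radiotherapy, but no analysis uses a second pre-treatment scan.

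**The concern.** Containment has a ceiling, and the planning scan sits on it. Every later scan carries differences in set-up, contouring and anatomy that the planning scan, compared with itself, cannot carry. These differences push containment in one direction only. A patient whose tumor does not change can therefore show a drop from planning to the first repeat scan and nothing afterwards.

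Section 9.4 measures the endpoints at baseline and then weekly, and item 5 does not say whether the planning scan enters as an ordinary time point. If it does, a single step is spread over the weeks and reads as progressive loss of containment during radiotherapy. The same step makes the first repeat scan look like the moment of change in item 6. Section 9.2 says that the study is meant to inform whether and when plans are re-calibrated, so an immediate step and a progressive drift need to be told apart.

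Target dose under the initial plan is expected to behave in the same way, because the plan was made on that scan. For volume the issue is narrower: true growth or shrinkage between simulation and first fraction is counted as change during treatment.

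**Working it through.** **Design figure.** 4 strata x 30 patients = 120, as stated. Section 9.2 says that the study is not powered, so there is no power figure to reproduce. The documents give no positional error, contouring error, tumor size, margin, simulation-to-start interval or pre-treatment growth. The values of these used below are assumptions.

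**1. Containment with no true change.** Assume a spherical GTV of radius 20 mm, an ITV wider by a fixed margin, and a random scan-to-scan shift with the same SD on each axis. Containment is the overlap of the two spheres divided by the GTV volume. The 95% cut is illustrative.

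| Margin | Shift SD per axis | Mean containment | Patients below 95% |
|---|---|---|---|
| 2 mm | 2 / 3 / 4 mm | 97% / 93% / 87% | 20% / 56% / 76% |
| 5 mm | 2 / 3 / 4 mm | 99.9% / 99% / 96% | 0.1% / 7% / 27% |

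The step is large with a tight container and small with a generous one. Where the CTV is the container, the lower row is the closer guide.

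**2. What item 5 makes of the step.** Take 100% at planning and a flat 93% afterwards. Slope = sum of (week - mean week) x containment / Sxx, where Sxx is the sum of squared deviations of week from its mean.
- Weeks 0 to 7: (-3.5 x 7)/42 = -0.58 points per week.
- Weeks 0, 2, 4, 6: (-3 x 7)/20 = -1.05 points per week.
- Weeks 0, 1, 2, 3: (-1.5 x 7)/5 = -2.1 points per week.

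The true on-treatment slope is zero in all three. Three repeat scans is the stated MR minimum (6.6, 9.2). On the log scale of item 5, ln(0.93) = -0.0726, and weeks 0 to 7 give (3.5 x -0.0726)/42 = -0.0060, about -0.6% per week. The transformation does not remove the effect.

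**3. Does comparing on-treatment scans with each other remove the noise?** Use the 2 mm margin and 3 mm SD, and let the GTV shrink inside the fixed baseline ITV.

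| GTV shrinkage | Mean containment | Patients below 95% |
|---|---|---|
| 0% | 92.6% | 56% |
| 20% | 96.4% | 27% |
| 44.3% (lung figure cited in 2.0) | 99.1% | 6% |

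With constant noise, shrinkage alone raises containment. The noise floor is not a constant that cancels.

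**4. Volume.** With contouring noise alone (CV 5% to 15%, 30 patients), the median change is about 0 and a two-sided 5% signed-rank test rejects in about 5% of runs. The average is not biased. Individual patients are still misread: 16%, 48% and 64% of stable patients show a change above 10% at CV 5%, 10% and 15%.

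True pre-treatment growth g does shift the result: observed reduction = 1 - (1 - 0.443)(1 + g). For g = 5%, 10%, 20% a true 44.3% reads as 41.5%, 38.7%, 33.2%. This only illustrates direction, since the documents give no g.

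**5. What the first on-treatment scan contains.** No scan is scheduled at the first fraction. If the 44.3% reduction were log-linear over 7 weeks (assumed), week 1 alone would bring 1 - 0.557^(1/7) = 8.0%. The first-scan step can thus hold real response as well as noise.

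**6. Precision cost of leaving out the planning scan.** The within-patient slope SE scales with 1/sqrt(Sxx), at equal residual SD. Weeks 0-7 against 1-7: sqrt(42/28) = 1.22. Weeks 0, 2, 4, 6 against 2, 4, 6: sqrt(20/8) = 1.58.

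**The case against.** The strongest reply is that the planning scan is the right reference for the question that matters most. The study asks whether a plan built on that scan stays valid, and drift before the first fraction is part of that error. This stands for Aim 2 and for item 6, and the reference should stay. It does not settle how a slope described as change during treatment should be estimated.

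Second, this is a descriptive pilot, item 5 is exploratory, and it does not state that the planning scan enters as an ordinary time point. Item 2 specifies no test of containment against 100%. All true, but the text leaves the model open, and in a descriptive study the estimates are the product.

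Third, subtracting the first-scan step could remove real early response. This also stands, so the step should be shown and not subtracted.

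Four stronger readings are tempting and are not supported:
- A reader might infer that every change measure is biased by noise. Volume noise is symmetric, and dose to normal organs can move either way.
- A reader might infer that comparing on-treatment scans with each other cancels the noise. Step 3 of the working shows that it does not when the GTV shrinks.
- A reader might take the note that baseline and eligibility procedures "may occur at any time from consultation until radiation therapy treatment begins" as the timing of the planning scan. That note concerns eligibility and consent; the evidence on timing is the simulation appointment in 2.0.
- A reader might attribute pre-treatment shrinkage to earlier chemotherapy, or set breathing excursions against the displacement cited in 2.0. No induction chemotherapy is described, 4D imaging is foreseen where breathing matters, and the cited 3.3 mm is a head-and-neck figure.

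**Conclusion.** The concern holds for containment and is worth acting on. Baseline containment is 100% by construction, so noise acts in one direction, and one trend through baseline and weekly values can show a decline with no on-treatment change. In the worked example the false slope is -0.58 points per week with seven weekly scans and -1.05 to -2.1 with three. It rests on an assumed fall to 93%; with a 5 mm margin the step is about 0.1 to 4 points. Item 6 can be pulled toward the first repeat scan for the same reason.

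Target dose under the initial plan is expected to follow containment; this is reasoned and not computed. For volume, only true change between simulation and first fraction is misattributed, and its size cannot be derived from the documents.

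**What to change.** Keep the planning scan as the reference for Aim 2 and for item 6. Add to 9.5:

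- **Items 1, 2, 4 and 5:** report the difference between the planning scan and the first on-treatment scan on its own line, with the days from planning scan to first fraction and from first fraction to that scan.
- **Item 5:** show the model with and without the planning scan, or with an indicator for it, side by side.
- **Interpretation:** state that the first-scan step mixes pre-treatment change, noise and early response and is not subtracted as pure noise. State also that the on-treatment containment trend is read beside the GTV volume trend, because shrinkage alone raises containment.
- **Item 6:** keep the present definition, and report whether the change was already present at the first on-treatment scan or progressed afterwards.

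The cost is SAP wording, two recorded intervals and a little more analysis, with no new scans. The slope without the planning scan is less precise: its SE is about 22% larger with seven weekly scans and about 58% larger with three, so both versions should be shown.

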## **2.0 BACKGROUND AND SIGNIFICANCE**

Radiation therapy is a form of treatment used to control many cancers including lung cancers, head and neck malignancies, cancers of the gastrointestinal tract and gynecological cancers. One important challenge of radiation treatment is the balance between delivering adequate radiation dose to the tumor while controlling for radiation induced toxicity. Radiation induced toxicity is caused by incidental radiation delivery to critical normal structures in proximity to the tumor. The amount of incidental radiation dose is dependent upon the tumor volume, location and margins needed to account for planning and setup error. The volumes are determined during radiation treatment planning and are based on patient imaging done during a simulation appointment prior to radiation treatment. In cancers with a propensity for movement secondary to respiratory motion, such as lung, and some gastrointestinal cancers, 4D CT planning is often implemented. This form of image guided treatment planning takes into account

